## Study Summary

Title	Rheumatoid arthritis memory B cells and Abatacept
Short Title	RAMBA
Protocol Number	IM101-768
BMS Protocol Number	IM101-768
Phase	Phase 4
Methodology	Open label
Study Duration	12 months
Study Center(s)	Single-center
Objectives	We will test the hypothesis that ABATACEPT treatment influences the levels of circulating autoimmune anti-citrullinated protein antigen (ACPA) memory B cells are central drivers of pathogenesis.
Number of Subjects	25
Diagnosis and Main Inclusion Criteria	Adults with Seropositive (CCP or ACPA) Rheumatoid Arthritis who are Naive to Biologic Disease-Modifying Antirheumatic Drugs
Study Product, Dose, Route, Regimen	Abatacept Time 0, Week 2, Month 1, 2, 3, 4, & 5 IV administration on Abatacept (7 infusions)
Duration of administration	6 months with active therapy followed by holding Abatacept for 6 months or until flare occurs while concurrent MTX or csDMARDs are continued.
Reference therapy	
Statistical Methodology	We will assess whether ABATACEPT challenge that induces clinical benefits are paralleled by reductions (i.e.,normalization) in the in vivo representation of disease-associated anti-citrullinated protein antigen (ACPA) memory B cells, and circulating autoantibody levels after 6 months of treatment.

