## **2 Study Objectives**

As a step toward a cure, we will directly assess the impact of a treatment on the underlying autoimmune disease process. Because Abatacept has unique mechanisms of action we believe that ABATACEPT treatment ameliorates RA clinical disease activity through beneficial effects on the pathologic breaches in adaptive immunity that are causal for disease. We will therefore conduct a prospective open therapeutic trial with adult seropositive (i.e., ACPA-positive) RA patients and perform intensive quantitative surveys of pathologic autoantigen-specific B cell memory.

We will test whether the clinical benefit induced by ABATACEPT treatment are paralleled by reductions (i.e., normalization) in the in vivo representation of disease-associated anti-citrullinated protein antigen (ACPA) memory B cells after 6 months of treatment. The corollary is to determine whether reductions of disease-associated memory B cells are the most meaningful marker of therapeutic response? ii) Hypothesis 2: The cessation of ABATACEPT treatment (i.e., dechallenge) with continued methotrexate therapy results in clinical flare, is then paralleled by reaccumulation in the bloodstream of disease-associated ACPA memory B cells.

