### **Secondary Objective**

We will correlate the relationships between co-primary endpoints over time and then confirm this relationship by dechallenge of Abatacept after induction of low disease activity at 24 weeks.

We will assess whether ABATACEPT therapy that induces clinical benefits, are paralleled by reductions (i.e., normalization) in the in vivo representation of disease-associated anti-citrullinated protein antigen (ACPA) memory B cells after 6 months of

[figure not shown]
treatment. This can be confirmed by dechallenge experiments in the approximately 70-80% we expect to be in low-disease activity at this time point. While MTX therapy will be maintained, little or no effect of MTX on memory B cell formation is expected as seen in Juvenile Idiopathic Arthritis.

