### 3 Study Design

#### 3.1 General Design

A phase IV open-label clinical trial in which each CCP/ACPA+ patient will be their own longitudinal control for the immunomodulatory activity of Abatacept. All patients will have blood collection, including for peripheral blood mononuclear cells (PBMC), PBMC RNA and plasma, at screening and at day 0 after which Abatacept will be initiated in concert with methotrexate or pre-existing csDMARD. Each patient will then be reevaluated at 3 months and 6 months. In all patients, Abatacept will be discontinued after 6 months. Patients who have flared or failed to achieve low disease activity at 6 months, will exit the trial except for one post study visit for lab work at 9 months.

In patients who have achieved low disease activity by DAS28-CRP (<3.2) or CDAI (<10), Abatacept will be held for 6 months or until a flare results. A flare is defined by an examination demonstrating a DAS28-CRP that is greater than an absolute value of 4.0) or a CDAI >15, both defining the mid-range of a moderate flare. Alternatively, a 30% increase in the absolute level of the DAS28-CRP or CDAI that result in measures of 3.2 and 10 respectively, will be considered evidence of a flare. If patients do not experience a flare after 6 months off Abatacept (by week 52) they will also exit the study after a final visit with an exit blood draw.

Overall, in this pilot study, patient screening will continue until 25 suitable patients are enrolled and started on therapy in the trial. We predict enrollment of 2-3 patients/month, and hence the study should be fully enrolled by month 14 with the expectation that 70-80% will achieve low disease activity at week 24 enabling 17-20

patients to be followed for flare following Abatacept dechallenge. This estimate is based on the observation that treat provides nearly 60% ACR 50 responses, despite the fact that patients were selected for evidence of erosive disease.

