### 3.2 Primary Study Endpoints

To assess the efficacy of Abatacept + csDMARD to induce low disease activity [DAS28-CRP (<3.2) or CDAI (<10) that can be maintained on csDMARD alone. A necessary co-primary objective is the relationship between clinical response and changes in B cell and antibody parameters that are unaffected by TNF-inhibition.

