### **4.3     *Subject Recruitment and Screening***

Eligibility will be based on specified inclusion and exclusion criteria, medical history, disease activity and safety assessments. Day 1 must occur within 28 days of signing the informed consent. Subjects that experience an acute infection or initiate treatment for latent TB may extend the screening period to 42 days.

Eligible subjects will have had symptoms and diagnosis of RA prior to signing the informed consent. Symptoms of RA are defined as pain, stiffness or swelling in joints which are typically inflamed in RA. Subjects must also have fulfilled criteria for rheumatoid arthritis by ACR/EULAR 2010 classification prior to signing informed consent.

Subjects treated with MTX must remain on a stable dose of oral methotrexate for at least 4 weeks prior to Day 1. The stable dose of oral MTX should be the maximum tolerated dose (minimum of 15 mg and maximum of 25 mg per week). A dose of methotrexate 7.5-12.5mg/week is permitted if intolerance to 15 mg or higher doses has been recorded in the source documents and the dose of oral methotrexate is stable for 4 weeks prior to randomization.

To minimize potential methotrexate toxicity, all subjects must receive folic acid, folinic acid, or leucovorin according to the manufacturer recommendations, methotrexate label instructions, and the local medical standard of care guidelines. Subjects receiving oral corticosteroids must be on a stable dose and at the equivalent of 10 mg prednisone daily for at least 4 weeks prior to randomization. Subjects may not have received an IM, IV or IA administration of a corticosteroid within 4 weeks prior to randomization.

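### After Month 6 no rule fixes csDMARD or steroid treatment and flare rests on scores alone, so a patient rescued before flare can be counted as maintained on csDMARD alone

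*Combined protocol and SAP*

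**What the plan says.** **Endpoint.** Section 3.2 asks whether abatacept plus csDMARD induces low disease activity (DAS28-CRP below 3.2 or CDAI below 10) "that can be maintained on csDMARD alone".

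**Background treatment after Month 6.** The Study Summary describes "holding Abatacept for 6 months or until flare occurs while concurrent MTX or csDMARDs are continued". Section 2 states the hypothesis "The cessation of ABATACEPT treatment (i.e., dechallenge) with continued methotrexate therapy results in clinical flare". The Secondary Objective adds "While MTX therapy will be maintained, little or no effect of MTX on memory B cell formation is expected". None of the three fixes a drug or a dose, and none mentions steroid.

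**Dose-stability rules.** These apply before treatment starts. Section 4.3 says "Subjects treated with MTX must remain on a stable dose of oral methotrexate for at least 4 weeks prior to Day 1" and "The stable dose of oral MTX should be the maximum tolerated dose (minimum of 15 mg and maximum of 25 mg per week". Sections 4.1 and 4.3 require a stable oral steroid dose, and bar intramuscular, intravenous and intra-articular steroid, for four weeks before screening, start of therapy or randomization. Section 5.5 permits established prednisone below 10 mg/day and hydroxychloroquine up to 400 mg/day, in a paragraph about who may enter. Section 5.1 rules out TNF antagonists and JAK inhibitors as concomitant drugs, but not another csDMARD.

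**Flare.** Section 3.1 has two limbs, both based on scores: "A flare is defined by an examination demonstrating a DAS28-CRP that is greater than an absolute value of 4.0) or a CDAI >15"; and "Alternatively, a 30% increase in the absolute level of the DAS28-CRP or CDAI that result in measures of 3.2 and 10 respectively". Patients without a flare leave the study at Week 52.

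**Analysis.** Sections 6.2 and 6.3 do not say how a patient whose background treatment changes is classified.

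**The concern.** The withdrawal phase is meant to show whether csDMARD can hold a response that abatacept plus csDMARD produced. That reading needs the background treatment to stay as it was, or a change in it to count against maintenance. The plan provides neither. If symptoms return and the clinician adds hydroxychloroquine, raises prednisone or injects a joint, the scores may stay below the flare limits because of that treatment. The patient then reaches Week 52 without a flare.

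The trial is open-label with no concurrent control, so the effect of rescue cannot be separated from that of the original regimen. The B-cell and antibody samples of the withdrawal phase are affected too: those taken after a change no longer reflect abatacept withdrawal alone. The Secondary Objective expects little or no methotrexate effect on memory B cells, but says nothing comparable about prednisone or hydroxychloroquine. Section 6.2 intends the results to inform the power of later studies, so an error here would carry forward.

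**Working it through.** **1. Patients at risk.** Section 3.1 plans 25 patients and expects 70-80% in low disease activity at Week 24. 25 × 0.70 = 17.5 and 25 × 0.80 = 20, which matches the stated 17-20.

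**2. Can a rescued patient stay unflared under the rules?** Take a hypothetical patient with DAS28-CRP 3.0 and CDAI 9 at Month 6, and assume the 30% rise is measured from Month 6 (Section 3.1 does not state the reference).
- Relative limb, DAS28-CRP: 1.3 × 3.0 = 3.9, below the absolute limit of 4.0.
- Relative limb, CDAI: 1.3 × 9 = 11.7, below the absolute limit of 15.

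For this patient, a DAS28-CRP from 3.2 up to 3.9 together with a CDAI from 10 up to 11.7 is outside low disease activity but is not a flare. Suppose treatment is increased in that band at Month 7, and the scores at Month 9 are 2.9 and 8. The patient has not flared and is again in low disease activity. Whether maintained means not flared or in low disease activity at the later visit, the scores alone classify the patient as maintained. This holds even if an examination was done before the rescue.

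**3. Routes to rescue.**
- Oral steroid: no on-study rule on changes. Even if the Section 5.5 limit is read as applying on study, a rise to a dose still below 10 mg/day is possible.
- Injected steroid: barred only before entry.
- Added csDMARD: not barred.
- Methotrexate: limited room, because Section 4.3 asks for the maximum tolerated dose. Section 5.5 mentions new starters at 20 mg/week; against the 25 mg maximum this leaves 25 − 20 = 5 mg/week, or 5/20 = 25%, for those who tolerate it.

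**4. Effect on the maintained proportion.** Per patient who is rescued and stays unflared to Week 52:
- 1/20 = 5.0 points; 1/17 = 5.9 points.
- With all 25 treated patients as denominator: 1/25 = 4.0 points.

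The documents give no rescue rate. Assuming 1 to 3 such patients, the shift runs from 1/20 = 5.0 to 3/17 = 17.6 points. If 10 of 20 appear maintained (also an assumption), reclassifying them gives:

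| Rescued patients | Maintained | Exact 95% interval |
|---|---|---|
| 0 | 10/20 = 50% | 27-73% |
| 1 | 9/20 = 45% | 23-69% |
| 2 | 8/20 = 40% | 19-64% |
| 3 | 7/20 = 35% | 15-59% |

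**The case against.** **The intent is stated.** Background treatment is to be continued and methotrexate maintained. That stands as intent and rules out planned withdrawal, but it sets no dose and gives no consequence for a change.

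**An added csDMARD is still csDMARD alone.** This is correct. Counting such a patient as maintained follows the wording, and calling it failure is a choice of estimand. A reader might infer that both routes break the endpoint definition; only the steroid route does. The csDMARD route changes what the result means.

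**Rescue would be seen.** A reader might infer that rescue between visits leaves no trace, because the Table of Events for remission or low disease activity shows Month 9 as the only scored visit after Month 6. The documents do not support that. The table duplicates the non-responders table and shows no blood sample at Week 48-52, although Section 3.1 promises an exit draw, so it may be a copying error. The companion table with flare has a flare visit and four-weekly visits, each with scores and a medication review, although it also marks abatacept infusions there and may not describe patients off the drug. Changes may well be observed. What is missing is a rule that uses them.

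**Prednisone is capped.** Section 5.5 does give a limit below 10 mg/day, but words it as a condition of entry. Read more broadly, it would exclude new or high-dose prednisone, yet it still would not say how a change is classified.

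**It is a pilot.** Section 6.1 says so, and Section 6.2 specifies no estimate or test for maintenance; the proportion used here is the natural summary of the endpoint, not one the plan names. One patient is small against an interval of 27-73%. This limits the importance of the point but does not remove it.

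**Conclusion.** The point holds. Followed exactly, the plan can classify a patient rescued before a score-defined flare as maintained on csDMARD alone. The upward shift is 5.0 to 5.9 percentage points for each such patient who stays unflared to Week 52, assuming 17-20 at risk; a patient who flares later adds nothing. How many there would be is unknown.

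A reader might infer that the bias must always favour maintenance. That is true of uncounted rescue taken by itself. But without a dose rule, methotrexate or prednisone may also be reduced, which could push patients towards flare and lower the proportion. The net direction cannot be settled from the documents. Because the gap lies in the classification of the primary endpoint and is cheap to close, it should be fixed, though at this sample size it does not by itself undermine the study.

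**What to change.** **Section 3.1.** From Month 6 until flare or Week 52, hold csDMARD and oral prednisone at the Month 6 drug and dose, and avoid intramuscular, intravenous and intra-articular steroid. Allow reductions for toxicity and clinically necessary rescue. Where possible, do a flare examination with scores before any rescue.

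**Sections 3.2 and 6.2.** Count any addition or increase for disease activity, including injected steroid, as not maintained from that date. Report the score-only classification as a sensitivity analysis, since csDMARD alone can also be read to include an adjusted csDMARD. Show the withdrawal-phase B-cell and antibody results with and without samples taken after a change.

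**Tables of Events.** Add a medication review at Month 6 to record the reference drugs and doses; neither table for responders marks one there. Record the date of and reason for later changes at the existing visits.

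**Cost.** Protocol wording and one review at an existing visit. The maintained proportion may be lower, and the restricted laboratory analysis will have fewer samples from an already small group. If Month 9 really is the next visit after Month 6, dates of changes in between will depend on recall or medical records over about three months.

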#### **NON-RESPONDERS TABLE OF EVENTS**

Procedure	Screening Period	DAY 1	WEEK 2	MONTH 1, 2, 3,4,5	MONTH 6/ET	MONTH 9	FOLLOW-UP (WEEK 48-52)
Medication review	X	X	X			X	X
Review of side effects	X	X					
Physical examination	X	X			X		
Height (screening only) & weight	X	X	X	X	X		
Blood sample(s) (Approx.166-176 - ml, or - 12tablespoons per visit )	X	X	X	X	X	X	
Urine sample	X	X	X	X	X		
Pregnancy test for women who can become pregnant	X	X	X	X			
Vital signs (temperature, blood pressure, heart rate (pulse))	X	X	X	X	X		
Assessments of your tender and swollen joints	X	X	X	X	X	X	
Assessments of disease activity	X	X	X	X	X	X	
Your Assessment of pain	X	X	X	X	X	X	
Rapid 3 patient questionnaire	X	X	X	X	X		
Abatacept infusion		X	X	X			
Adverse events		X		X	X	X	X

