**REMISSION OR LOW DISEASE ACTIVITY TABLE OF EVENTS WITH FLARE**

Procedure	Screening Period	DAY 1	WEEK 2	MONTH 1,2,3,4,5	MONTH 6/ET	FLARE	EVERY 4 WEEKS	FOLLOW-UP (WEEK 48-52)
Medication review	X	X	X	X		X	X	X
Review of side effects	X	X				X		
Physical examination	X	X			X	X		
Height (screening only) & weight	X	X		X	X	X	X	
Blood sample(s) (Approx.166-176 - ml, or - 12 tablespoons per visit )	X	X		X	X	X	X	
Urine sample	X	X		X	X	X	X	
Pregnancy test for women who can become pregnant	X	X		X	X	X	X	
Vital signs (temperature, blood pressure, heart rate (pulse))	X	X		X	X	X	X	
Assessments of your tender and swollen joints	X	X		X	X	X	X	
Assessments of disease activity	X	X		X	X	X	X	
Your Assessment of pain	X	X		X	X	X	X	
Rapid 3 patient questionnaire	X	X		X	X	X	X	
Abatacept infusion		X	X	X		X	X	
Adverse events		X		X	X	X	X	X

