### 3.3 Secondary Study Endpoints

We will correlate the relationships between co-primary endpoints over time and then confirm this relationship by dechallenge of Abatacept after induction of low disease activity at 24 weeks.

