#### **5.10 *Visit 2***

#### **5.11 *etc.***

### **6 Statistical Plan**

#### **6.1 *Sample Size Determination***

Not applicable, this is a pilot study

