#### **6.2 *Statistical Methods***

These studies are considered exploratory and will enable power analyses for subsequent larger studies. We anticipate that clinical responders will concurrently have more than 25% decreases in IgG anti-CCP3 levels (ANOVA). The mean change in IgG anti-CCP levels in responders versus non-responders will be analyzed by t-test. A proportional decrease in the estimated level of IgG anti-CCP3 secreting recirculating memory B cells is predicted as well. Clinical non-responders are predicted to not have a significant change. No significant effects on total IgG, IgA or IgM are anticipated. In a recent report with cross-sectional analyses we documented highly significant correlations  $r=0.57$   $p=0.0033$  between ACPA and memory B cell levels in studies of 24 RA patients (11). With longitudinal analyses we anticipate that relationships should require fewer subjects to document correlations between shifts in clinical activity and ACPA IgG and ACPA-memory B cell levels overtime. We will

assess non-parametric paired-sample comparisons by Spearman correlations, and longitudinal measurements using paired t test, with Prism v6.0e (GraphPad, La Jolla, CA). P<0.05 will be considered significant.

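### Section 3.1 and the three event tables disagree on when blood is drawn, by up to 664-880 mL per patient to Month 6, and the exit draw is missing from its table

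*Combined protocol and SAP*

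**What the plan says.** Section 3.1 (General Design) describes blood collection for mononuclear cells, "PBMC RNA and plasma, at screening and at day 0 after which Abatacept will be initiated". It continues: "Each patient will then be reevaluated at 3 months and 6 months". That second sentence does not mention blood. For later visits, section 3.1 gives patients who flared or did not reach low disease activity one laboratory visit at 9 months. Patients without a flare by week 52 have a final visit with an exit blood draw.

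The three event tables that follow each have a single blood row:

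- **Non-responders:** "Blood sample(s) (Approx.166-176 - ml, or - 12tablespoons per visit", ticked at screening, Day 1, Week 2, Months 1 to 5, Month 6 and Month 9.
- **Remission or low disease activity, no flare:** the same volume and the same ticks. Nothing is ticked for blood at the Week 48-52 follow-up.
- **Remission or low disease activity, with flare:** "Blood sample(s) (Approx.166-176 - ml, or - 12 tablespoons per visit", ticked at screening, Day 1, Months 1 to 5, Month 6, at flare and every 4 weeks. Week 2 is not ticked.

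No section divides the volume into safety and research blood.

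On use of the samples, section 2 names "anti-citrullinated protein antigen (ACPA) memory B cells after 6 months of treatment". Section 3.3 says "We will correlate the relationships between co-primary endpoints over time". Section 6.2 plans Spearman correlations and "longitudinal measurements using paired t test". Neither 3.3 nor 6.2 attaches an immune measurement to Week 2 or to Months 1, 2, 4 or 5.

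**The concern.** A site works from the event tables. Followed as printed, they take the full volume at Week 2 and at Months 1, 2, 4 and 5, where section 3.1 describes no evaluation and no immune analysis is specified. One undivided row leaves the site unable to tell a small safety sample from the large research draw.

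Two further problems bear on the data:

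- The tables are distinguished by Month 6 response and later flare, yet they differ at Week 2, when neither is known. A site cannot tell which one to follow, so Week 2 samples may be taken in some patients and not in others.
- The no-flare table omits the exit draw that section 3.1 requires. That sample is the last off-drug measurement in patients who stay well, and the dechallenge hypothesis in section 2 needs it as the counterpart to the flare sample. With 25 patients enrolled and 17-20 expected to enter dechallenge, few such samples can be lost.

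**Working it through.** **Inputs.** Volume per visit V = 166-176 mL (all three tables). Draws are counted from the ticks in each table. Section 3.1 gives screening, day 0, Month 3 and Month 6. Section 6.1 ("Not applicable, this is a pilot study") supplies no sample size quantity, and none is needed here.

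**The plan's own figure.** Taking 14.787 mL per US tablespoon (a unit conversion, not from the documents), 166/14.787 = 11.2 and 176/14.787 = 11.9. The stated 12 tablespoons is consistent with the upper end of the range, so the per-visit volume is not a unit slip.

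**Draws from screening to Month 6.**

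- Non-responder and no-flare tables: screening + Day 1 + Week 2 + five monthly visits + Month 6 = 9.
- Flare table: the same without Week 2 = 8.
- Section 3.1, with blood inferred at both re-evaluations: 4.

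**Volume = draws × V.**

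- 9 × 166 = 1,494; 9 × 176 = 1,584 mL.
- 8 × 166 = 1,328; 8 × 176 = 1,408 mL.
- 4 × 166 = 664; 4 × 176 = 704 mL.

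**Ratio to the section 3.1 schedule.** 9/4 = 2.25 and 8/4 = 2.0. These apply to the cumulative total to Month 6.

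**Excess.**

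- Non-responder and no-flare tables: 5 × 166 = 830 to 5 × 176 = 880 mL.
- Flare table: 4 × 166 = 664 to 4 × 176 = 704 mL.
- Across the tables: 664-880 mL.

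**Why this is a maximum.** If an extra visit needs s mL for safety tests or CRP anyway, the avoidable volume is (number of extra draws) × (V − s). The documents do not give s, so it has to be assumed:

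- s = 0: 664-880 mL, as above.
- s = V/2, five extra draws: 5 × 83 = 415 to 5 × 88 = 440 mL.
- s = V: nothing is avoidable.

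**After Month 6.**

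- Non-responders: the Month 9 draw appears in both the text and the table.
- No flare: the table ticks Month 9, which section 3.1 does not name for these patients, and leaves out the exit draw, which it does. Both sources give one draw after Month 6 (10 in all in the table, 5 in the text), but at different visits.
- Flare: the table adds V at flare and every 4 weeks. Section 3.1 gives no blood schedule for this period.

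**The case against.** The strongest reply is that section 3.1 is a summary. It nowhere says that research blood is taken only at the visits it lists, and a summary naming fewer visits than the tables may be incomplete rather than contradictory. This is a pilot, and how densely to sample in exploratory work is a legitimate choice. The Primary and Secondary Objectives, section 3.3 and section 6.2 all speak of change or correlation over time. The tables schedule joint counts and disease activity wherever blood is ticked before Month 6, and DAS28-CRP needs a CRP sample.

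Much of this stands, and it rules out several stronger readings that a reader might infer:

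- **That the interim draws serve no endpoint.** A general longitudinal purpose is stated. What is missing is a use specific to those visits.
- **That every table takes blood at every visit to Month 6.** The flare table does not tick Week 2.
- **That 664-880 mL is all unnecessary.** Some blood is needed at the extra visits, and the documents give no split.
- **That section 3.1 allows only two draws before Month 6** (332-352 mL). Blood is named only at screening and day 0, but a memory B cell endpoint after 6 months of treatment requires a Month 6 sample. Four draws is the fairer comparison.
- **That patients will become anaemic or refuse draws.** The documents give no haemoglobin threshold, refusal rate or dropout figure.
- **That patients are not told the total volume.** The consent form is an attachment and was not available for this review.

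The reply does not explain the Week 2 difference between tables, the missing exit tick or the undivided row.

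**Conclusion.** The text and the tables do not agree on blood sampling, and the tables do not agree with one another. To Month 6, a site following the tables draws up to 2.0 times (flare table) or 2.25 times (the other two) the volume implied by section 3.1. The difference is at most 664-704 mL or 830-880 mL per patient.

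This rests on three assumptions: the full stated volume is taken at every ticked visit; the same volume applies at the section 3.1 time points; and Months 3 and 6 include sampling. The Week 2 discrepancy and the omitted exit draw need none of these assumptions.

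The point should be corrected because it determines what is drawn from patients and whether the exit sample is collected. It does not show that the endpoints are invalid or that interim sampling is unjustified.

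**What to change.** Reconcile section 3.1 with the three event tables. Specifically:

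- Split the blood row into a safety row and a research row, with a volume for each visit.
- Take the full research volume only at visits the sponsor designates for immune evaluation. Day 0, Month 6, flare and exit should be explicitly kept. Limiting research blood to visits where section 3.1 or 6.2 names an immune test would not work: section 6.2 names no visits, and section 3.1 does not name blood at Month 6 or flare.
- For any interim research draw that is kept, state in section 6.2 the analysis that uses it.
- Make the three tables identical up to Month 6, including Week 2.
- Add the exit draw to the no-flare table, and settle whether these patients also have a Month 9 draw.
- State the cumulative volume per patient, and check that the consent form matches.

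The cost is a table edit, a few sentences in sections 3.1 and 6.2, and any matching consent wording. The downside is the possible loss of interim research samples that have no visit-specific analysis; the sponsor can keep them by stating their purpose.
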